APPENDIX C

Definition of Women of Childbearing Potential and Acceptable and Unacceptable Forms of Contraception

Women of childbearing potential are defined as follows:

- Patients with regular menses
- Patients with amenorrhea, irregular cycles, or using a contraceptive method that precludes withdrawal bleeding
- Women who have had a tubal ligation

Women are considered not to be of childbearing potential for the following reasons:

- The patient has undergone hysterectomy and/or bilateral oophorectomy.
- The patient is post-menopausal defined by amenorrhea for at least 1 year in a woman >45 years old.

Women of childbearing potential are required to use two forms of acceptable contraception, including one barrier method, during their participation in the study and for 12 months following discontinuation of GDC-0449.

The following are acceptable forms of barrier contraception:

- Latex condom (always used with spermicide)
- Diaphragm (always used with spermicide)
- Cervical cap (always used with spermicide)

The following are acceptable forms of secondary contraception, when used with a barrier method:

- Tubal ligation
- Partner's vasectomy
- Hormonal contraception including birth control pills, patches, rings, or injections, *with the exception of the progesterone-only "minipill"*
- Intrauterine device (non-progesterone T)
- Vaginal sponge (containing spermicide)

In addition, 100% commitment to abstinence is considered an acceptable form of contraception.

The following are **unacceptable** forms of contraception for women of childbearing potential:

- IUD progesterone T
- *Progesterone-only “minipill”*
- Female condom
- Natural family planning (rhythm method) or breastfeeding
- Fertility awareness
- Withdrawal
- Cervical shield

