study participation, and for at least 24 months post-treatment for female patients and for 2 months for male patients. For appropriate methods of contraception considered acceptable [see Appendix C](#). Should a woman become pregnant or suspect she is pregnant while participating in this study, she should inform her treating physician immediately.

- 3.1.11 **Pregnancy Testing.** Women of childbearing potential are required to have a negative serum pregnancy test (with a sensitivity of at least 25 mIU/mL) within 7 days prior to initiation of GDC-0449 treatment (serum or urine). A pregnancy test (serum or urine) will be administered every 4 weeks while on study within the 24-hour period prior to the administration of GDC-0449. A positive urine test must be confirmed by a serum pregnancy test. Prior to dispensing GDC-0449, the investigator must confirm and document the patient's use of two contraceptive methods, dates of negative pregnancy test, and confirm the patient's understanding of the teratogenic potential of GDC-0449.

Women of childbearing potential are defined as follows:

- Patients with regular menses
- Patients with amenorrhea, irregular cycles, or using a contraceptive method that precludes withdrawal bleeding
- Women who have had a tubal ligation

Women are considered not to be of childbearing potential for the following reasons:

- The patient has undergone hysterectomy and/or bilateral oophorectomy.
- The patient is post-menopausal defined by amenorrhea for at least 1 year in a woman > 50 years old.
- The patient has permanent premature ovarian failure confirmed by specialist gynecologist

- 3.1.11 Ability to understand and the willingness to sign a written informed consent document.

- 3.1.12 In accordance with French Regulatory Authorities: Patients with French Social Security in compliance with the French law relating to biomedical research (Huriet Law 88-1138 and related decrees).

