Female patients are required to use two forms of acceptable contraception (refer to [Appendix C](#)), including one barrier method during participation in the study and respectively for the 2 and 24 months following the last dose for both male and female patients. All patients should receive contraceptive counseling either by the investigator, or by an obstetrician (OB)/gynecologist or other physician who is qualified in this area of expertise. If a woman of childbearing potential believes that her contraceptive method has failed, emergency contraception should be considered. If a patient is suspected to be pregnant, GDC-0449 should be immediately discontinued. In addition, a positive urine test must be confirmed by a serum pregnancy test. If it is confirmed that the patients is not pregnant, the patient may resume dosing with GDC-0449.

If a female patient becomes pregnant during therapy or within 24 months after the last dose of GDC-0449, or if the female partner of a male patient exposed to the drug becomes pregnant while the male patient is receiving GDC-0449 or within 2 months after the last dose of GDC-0449, the investigator must be notified in order to facilitate outcome follow-up.

Abortion, whether accidental, therapeutic, or spontaneous, should always be classified as serious. Any congenital anomaly/birth defect in a child conceived during the study or within 24 months after the last dose of GDC-0449 to a female patient or to a female partner of a male patient

exposed to the agent during treatment or within 2 months after the last dose of GDC-0449 should be recorded and reported as an SAE.

- Female patients should not breastfeed a baby while on this study.
- Female patients must NEVER donate ova while being treated with GDC-0449.
- All sexually active male subjects (including those who have undergone vasectomy) should utilize a barrier form of contraception during study treatment and for 2 months after the last dose as it is not known whether GDC-0449 that may be present in seminal fluid would cause teratogenic effects in a fetus born to the female partner of a male subject. Males should also not donate sperm during treatment or up to 2 months after the last dose.
- All patients are prohibited from donating blood for 24 months after the last dose of GDC-0449.

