SKIN AND SUBCUTANEOUS TISSUE DISORDERS - Hyperhidrosis; Nail ridging; Pruritus; Rash acneiform; Rash maculo-papular; Skin and subcutaneous tissue disorders - Other (hair color changes); Skin and subcutaneous tissue disorders - Other (psoriasis); Skin and subcutaneous tissue disorders - Other (skin exfoliation); Skin ulceration; Stevens-Johnson syndrome

VASCULAR DISORDERS - Hypertension; Hypotension; Thromboembolic event; Vasculitis

Note: GDC-0449 (Vismodegib) in combination with other agents could cause an exacerbation of any adverse event currently known to be caused by the other agent, or the combination may result in events never previously associated with either agent.

Additional Adverse Events

Teratogenic Effects of GDC-0449

Studies have demonstrated that inhibition of the Hh pathway in embryos results in brain, facial, and other midline defects, including holoprosencephaly or microcephaly, cyclopia, absent nose, cleft palate, tooth abnormalities, and bone development abnormalities (Bale, 2002).

GDC-0449 may cause embryo-fetal death or severe birth defects when administered to a pregnant woman. Hh pathway inhibitors such as GDC-0449 have been demonstrated to be embryotoxic and/or teratogenic in multiple animal species and can cause severe midline defects, missing digits, and other irreversible malformations in the developing embryo or fetus. GDC-0449 must not be used during pregnancy, except in severe life-threatening cases, where the potential benefit to the patient outweighs the risk to the fetus.

Both women of childbearing potential and men must agree to use two methods of contraception (i.e., barrier contraception and another method of contraception) prior to study entry, for the duration of study participation, and for 24 months following treatment for female patients and for 2 months for male patients.

Women of childbearing potential are defined as follows:

- Patients with regular menses
- Patients with amenorrhea, irregular cycles, or using a contraceptive method that precludes withdrawal bleeding
- Women who have had a tubal ligation

Women are considered not to be of childbearing potential for the following reasons:

- The patient has undergone hysterectomy and/or bilateral oophorectomy.
- The patient is post-menopausal defined by amenorrhea for at least 1 year in a woman > 45 years old.

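### Appendix C stops women's contraception at 12 months after the last dose instead of 24, and Appendix C and section 7.1 set the post-menopausal age at over 45 instead of over 50

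*Combined protocol and SAP*

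**What the plan says.** Contraception after the last dose, for women:

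- Section 3.1.10, and the matching synopsis criterion: "for at least 24 months post-treatment for female patients and for 2 months for male patients".
- Section 5.2.1: "respectively for the 2 and 24 months following the last dose for both male and female patients", which, read in order, gives men 2 months and women 24.
- Section 7.1 (teratogenic effects): "for 24 months following treatment for female patients and for 2 months for male patients". A later paragraph of the same section repeats 24 months for women of childbearing potential and refers to Appendix C.
- Appendix C: two forms, one of them a barrier method, "during their participation in the study and for 12 months following discontinuation of GDC-0449".

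Post-menopausal status, which takes a woman out of the childbearing-potential group:

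- Section 3.1.11 (Pregnancy Testing), and the matching synopsis criterion: "amenorrhea for at least 1 year in a woman > 50 years old".
- Section 7.1: "amenorrhea for at least 1 year in a woman > 45 years old".
- Appendix C: "amenorrhea for at least 1 year in a woman >45 years old".

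The background safety profile in section 2.2 also gives 12 months, and points to Appendix C as it does so.

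**The concern.** The protocol describes hedgehog inhibitors as embryotoxic or teratogenic in several animal species and warns of fetal death and severe birth defects. The length of contraception and the definition of who needs it are therefore safety instructions, and each should have one value.

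Appendix C could be taken as the authority on both. Its heading reads "Definition of Women of Childbearing Potential and Acceptable and Unacceptable Forms of Contraception", and it states its own requirement as well as listing methods. A site using it as the working reference would tell a woman she may stop contraception a year before the eligibility criterion allows.

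The age limit matters during treatment. A woman in the disputed age band is of childbearing potential under section 3.1.11 but not under section 7.1 or Appendix C. Under the looser definition, the pregnancy tests in sections 3.1.11 and 5.2.1 would not be applied to her, and the two-method rule in section 3.1.10 might not be.

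**Working it through.** The plan gives no figure to reproduce. The check compares every place that states one of the two values.

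| Place | Women: months after last dose | Post-menopausal age |
|---|---|---|
| Synopsis, inclusion criteria 10 and 11 | 24 | over 50 |
| Sections 3.1.10 and 3.1.11 | 24 | over 50 |
| Section 5.2.1 | 24 | not stated |
| Section 7.1 | 24 (stated twice) | over 45 |
| Appendix C | 12 | over 45 |
| Section 2.2 (background) | 12 | not stated |

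**Which values govern.** For duration, 24 months is in the eligibility criteria and is repeated in the treatment and safety sections. The 12-month text in section 2.2 says the drug's teratogenic potential had not been investigated, whereas sections 3.1.10 and 7.1 report demonstrated teratogenicity for the class. The 12 months therefore looks like a leftover; that is an inference. For age, the places split two against two. Over 50 is taken as governing because it is in the eligibility criteria and is the stricter value.

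**Duration.** 24 − 12 = 12 months omitted; 12 / 24 = 50% of the window.

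**Age.** In completed years, over 45 but not over 50 means 46, 47, 48, 49 and 50: five years of age.

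**Pregnancy tests for a woman in that band.** At the 4-week interval in section 3.1.11, 52 / 4 = 13 tests per 52 weeks on treatment, plus the baseline test. Footnote b of the study calendar asks for at least one a month, so at least 12 a year.

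**Number of women affected.** Not derivable. Section 13.2 plans 45 patients, with no split by sex or age.

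**Related reporting windows.** Section 7.3.4 uses 12 months in one provision on pregnancies generally (follow-up to outcome) and in three that name female patients (exposure form, birth-defect report, abortion report). Sections 5.2.1 and 7.1 use 24 months for notifying pregnancies in female patients and for birth-defect SAEs.

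**The case against.** **The correct duration is hard to miss.** Sections 3.1.10, 5.2.1 and 7.1 cite Appendix C for contraceptive methods and give 24 months alongside. This makes the error less likely to be acted on, but Appendix C still states a shorter requirement under a heading that covers the definition, and section 2.2 ties its 12 months to it.

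**The test rule and the age limit of 50 sit together in section 3.1.11.** A site applying the rule has the stricter definition in view, and eligibility is verified at registration (section 4.2). Section 14.2.2 also calls for a 100% check of selection criteria. These controls may catch a misclassification at entry. For the period after treatment they offer less: documentation of two methods is tied to dispensing, and the 100% list does not name contraception after the last dose. The general duty in 14.2.2 to check protocol compliance remains, but the protocol itself holds two values.

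**Section 5.2.1 asks female patients for two methods without limiting this to childbearing potential.** Read literally, it covers a woman of 46 to 50 under either age limit. However, the neighbouring text on testing and section 7.1 do carry that limit, so the position is mixed. The loss of pregnancy tests is the firmer consequence.

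**The reporting windows in section 7.3.4 are largely backstopped.** Section 7.3.3 requires birth-defect reports with no time limit. Section 7.3.4 itself requires a report of any possible prenatal exposure and a Grade 4 pregnancy report, neither with a limit. Section 7.7 asks for pregnancy reports on confirmation, and covers SAEs during follow-up and for 30 days afterwards if likely research-related. This stands, so the 7.3.4 windows are a secondary matter.

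**Conclusion.** The concern holds. Appendix C conflicts with the eligibility criteria on both duration and age; section 7.1 conflicts on age only. Followed as written, Appendix C removes half of the women's post-treatment contraception window. The looser age limit takes amenorrheic women aged 46 to 50 out of the childbearing-potential group, unless another exemption already applies to them. Few women may be affected, but the possible harm is severe and irreversible, and correction is cheap. It should be fixed.

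This rests on taking 24 months and over 50 as the intended values, and on a site using Appendix C or section 7.1 as its reference. It implies no fault in the 2-month rule for men, the reporting windows for partners, or the 3-month form provision in section 7.3.4. The Simon design figures are untouched.

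**What to change.** Essential changes:

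- Appendix C: 12 months becomes 24, and over 45 becomes over 50.
- Section 7.1: over 45 becomes over 50.

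Alignment in the same amendment:

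- Copy the premature-ovarian-failure exemption from section 3.1.11 into both places, for consistency only. Its absence there errs on the strict side.
- Section 7.3.4: bring the 12-month windows for female patients to 24 months, with CTEP agreement if needed, since that section follows NCI procedures.
- Section 2.2: update to 24 months for women and 2 months for men.
- Check that the patient information sheet, which is not in the copy reviewed, gives the same values.

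The cost is a wording amendment and re-issue to sites. It adds no burden on patients beyond what sections 3.1.10 and 3.1.11 already impose.

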APPENDIX D

POSSIBLE PRENATAL EXPOSURE TO TERATOGEN REPORT

Attach to CTEP-AERS 5-day report

| | | |
|--|---|---|
| Possible Prenatal Exposure to Teratogen Report AdEERS Ticket Number: _____ | | Study #: SAE [contact] Alternate [contact] |
| Initial Report Date:  -  -  | Follow-up Report Date:  -  -  | |
| Principal Investigator: | Reporter: | |
| Reporter Telephone #: | Reporter FAX #: | |
|       Investigator Number |       Subject Number |    Subject Initials |
| Complete all of the investigator and subject number boxes provided. Use leading zeros, when necessary, to complete all expected boxes. Example: Investigator #407 would be filled in as:      | | Record the first letter of the subject's first, middle and last name, in that sequence. If the subject has no middle name, enter a dash. Example:    |
| Subject's Sex:  Female  Male | Subject's Weight: _____ kg | Subject's Date of Birth:  -  -  |
| Subject's Ethnicity (check one only):  Hispanic or Latino  Not Hispanic or Latino  Not Available | | |
| Subject's Race (check all that apply):  American Indian or Alaska Native  Asian  Black or African American  Native Hawaiian or Other Pacific Islander  White  Not Available | | |
| Study Drug: GDC-0449 | Study Drug Start Date:  -  -  Study Drug Stop Date:  -  -  OR  Study Drug Continuing | |
| Dose: | Route: ORAL | Frequency: QD Kit #: |
| First Day of Last Menstrual Period:  -  -  | | Estimated Date of Delivery:  -  -  |
| Method of Contraception (check all that apply):  Oral Contraceptive Pills  Condoms  Periodic Abstinence  Progestin Injection or Implants  Spermicide  Diaphragm  Intrauterine Device (IUD)  Tubal Ligation  Other, specify: _____ | | |
| Reproductive History:  Gravida _____  Para _____ | | |
| Tests performed during pregnancy:  None  Unknown  CVS Results:  Normal  Abnormal  Amniocentesis Results:  Normal  Abnormal  Ultrasound Results:  Normal  Abnormal | | |
| Pregnancy Outcome Was pregnancy interrupted?  Yes  No If yes, specify:  Elective Termination  Spontaneous Abortion  Ectopic Date of Termination:  -  -  If pregnancy was not terminated, specify pregnancy outcome (and provide infant outcome information)  Vaginal Birth:  Premature  Term OR  C-Section:  Scheduled  Emergency Date of Delivery:  -  -  Infant outcome information:  Normal  Abnormal | | |
| Additional Case Details (if needed): | | |
| Note: Report possible teratogen exposure to AdEERS within 24 hours. See Protocol Section 11.3.1 for instructions. Attach this form to the complete 5-day AdEERS report. | | |

7.3.5

APPENDIX E

| |
|--------------------------------|
| CTEP-assigned Protocol # _____ |
| Local Protocol # _____ |

PATIENT'S MEDICATION DIARY

Today's date _____

Agent: **GDC-0449**

Patient Name _____ (*initials acceptable*)

Patient Study ID _____

INSTRUCTIONS TO THE PATIENT:

1. Complete one form for each cycle of treatment.
2. You will take **GDC-0449** capsules once daily. You should take the capsules at approximately the same time each day.
Dose: take one 150 mg capsule.
3. Record the date, the number of capsules of each size of capsule that you took, and when you took them.
4. If you have any comments or notice any side effects, please record them in the Comments column.
5. Please bring this form and your bottles of **GDC-0449** capsules when you return for each appointment.

| Day | Date | Time of dose | # of capsules taken | Comments |
|-----|------|--------------|---------------------|----------|
| | | | 150 mg | |
| 1 | | | | |
| 2 | | | | |
| 3 | | | | |
| 4 | | | | |
| 5 | | | | |
| 6 | | | | |
| 7 | | | | |
| 8 | | | | |
| 9 | | | | |
| 10 | | | | |
| 11 | | | | |
| 12 | | | | |
| 13 | | | | |
| 14 | | | | |
| 15 | | | | |
| 16 | | | | |
| 17 | | | | |
| 18 | | | | |
| 19 | | | | |
| 20 | | | | |
| 21 | | | | |
| 22 | | | | |
| 23 | | | | |
| 24 | | | | |
| 25 | | | | |
| 26 | | | | |
| 27 | | | | |
| 28 | | | | |

Patient's signature

Physician's Office will complete this section:

1. Date patient started protocol treatment _____
2. Date patient was removed from study _____
3. Patient's planned total daily dose _____
4. Total number of capsules taken this month _____
5. Physician/Nurse/Data Manager's Signature _____

**APPENDIX F
REGISTRATION FORM**

| | |
|---|---|
|  
INSTITUT BERGONIE Center Régional de Lutte Contre le Cancer de Bordeaux et du Sud-Ouest [name] [name]
 | 
IHC study (Inhibition of Hedgehog in Chondrosarcomas)
 |
| 
INCLUSION REQUEST FORM
 | |

| | |
|---|----------------------------------|
| 
Investigational site
 | |
| 
N° Center : 
 | 
Investigator:
 |
| 
Tel: 
 | 
Fax: 
 |

| | | |
|--|---|---|
| 
Patient
 | | |
| 
Patient's initial:   Name First
 | 
Date of Birth:  
 | 
Sex:  M  F
 |
| 
Confirmation of eligibility criteria:  Yes  No
 | | |
| 
Date foreseen for protocol treatment start: 
 | | |
| 
Date of signed consent patient :  
 | 
To confirm inclusion, signed investigator:
 | |

| |
|--|
| 
Fax this form, copy of biological result and signed consent patient to Clinical Trial and Epidemiology Unit / Institut Bergonié Fax: [name] From Monday to Friday : 9.00 to 17.00 Contact : [name] (AEC) [contact] – Mail: [contact]
 |
| 
Patient identification in this study (coordinator center): 
 
Date of inclusion : 
 |

APPENDIX G: TOXICITY ENDPOINTS (CTEP CTCAE Version 4.0)

TOXICITY EVALUATION CRITERIA (CTEP CTCAE Version 4.0)

You can download this document in PDF:

<http://ctep.info.nih.gov/reporting/ctc.html>

APPENDIX HA: REPORTING OF AN EXPECTED SERIOUS ADVERSE EVENT (E - SAE)

Notification Of A Serious Adverse Event Form To be faxed to Pharmacovigilance BECT – [name]

| | | | |
|--|---|----------------------------|---------------------------------------|
| PROTOCOL: CHONDROG | EUDRACT: 2010-019817-20 | COUNTRY: FRANCE | |
| SPONSOR : INSTITUT BERGONIE | | INVESTIGATOR SITE : | SITE N° [][] |
| DATE OF THIS REPORT : [][]/[][]/[][][][] | INITIAL REPORT  | FOLLOW-UP REPORT N° [][] | FINAL REPORT  |

1. PATIENT IDENTIFICATION

INCLUSION N° [][] SURNAME (2 LETTERS): [][] 1ST NAME (2 LETTERS): [][] DATE OF BIRTH: [][]/[][]/[][][][]
 TREATMENT ARM: [][] DOSE LEVEL (PHASE I STUDY): [][]
 Sex: F M WEIGHT (KG): [][] HEIGHT (CM): [][] BODY SURFACE AREA (M²): [][] . [][]

2. INFORMATION ON EVENT

DATE OF ONSET: [][]/[][]/[][][][] TOXICITY (GRADE NCI-CTCAE): 1 2 3 4 5
 DIAGNOSIS OR MAIN SYMPTOMS: **only one diagnosis or one symptom (except for linked symptom)**

.....
 DESCRIBE EVENT AND TREATMENT GIVEN (INCLUDING RELEVANT TEST/LAB DATA):

| | |
|---|---|
| <h4>3. SERIOUSNESS CRITERIA</h4> 
 DEATH, DATE OF DEATH: [][]/[][]/[][][][]
 
 LIFE-THREATENING
 
 REQUIRING/PROLONGING HOSPITALIZATION (> 24h): DATE OF ADMISSION: [][]/[][]/[][][][]
 
 PERSISTANT/SIGNIFICANT DISABILITY/INCAPACITY
 
 CONGENITAL DISORDER/BIRTH DEFECT
 
 MEDICALLY RELEVANT
 | <h4>4. OUTCOME</h4> 
 ON GOING EVENT
 
 RECOVERED WITHOUT SEQUELLA,  UNKNOWN OUTCOME
 
 RECOVERED WITH SEQUELLA, ↗ DATE [][]/[][]/[][][][]
 
 SPECIFY SEQUELLA:
 
 DEATH RELATED TO THIS EVENT, ↗ DATE [][]/[][]/[][][][]
 
 DEATH UNRELATED TO THIS EVENT, ↗ DATE [][]/[][]/[][][][]
 
 CAUSE OF DEATH:
 
 OR CAUSE UNKNOWN 
 
 AUTOPSY : YES  NO 
 
IF PATIENT WAS HOSPITALIZED: DATE OF END OF HOSPITALIZATION: [][]/[][]/[][][][]
 
 OR PATIENT STILL HOSPITALIZED AT THE TIME OF THIS REPORT 
 |
|---|---|

FOR IMP TRIALS ⇨ COMPLETE SECTION 5 FOR RADIOTHERAPY TRIALS ⇨ COMPLETE SECTION 6 FOR OTHER IMP TRIALS ⇨ COMPLETE SECTION 7

5. IMP (INVESTIGATIONAL MEDICINAL PRODUCT(S), INCLUDING COMBINED RADIOTHERAPY / SURGERY...) TICK IF NA

| INVESTIGATIONAL PROCEDURE(S) INDICATE THE INTERNATIONAL COMMON DENOMINATION OF THE IMP & OTHER COMBINED | ROUTE | SAE CYCLE NUMBER | DATES | | DOSE & UNIT | | | |
|--|-------|------------------|---|--|-----------------------------------|------|--|------|
| | | | DATE OF FIRST ADMINISTRATION/USE (1ST DAY OF CYCLE 1) | DATE OF LAST ADMINISTRATION/USE BEFORE SAE | LAST DOSE ADMINISTERED BEFORE SAE | | CUMULATIVE DOSE SINCE THE 1ST ADMINISTRATION | |
| | | | | | DOSE | UNIT | DOSE | UNIT |
| N°1 | | | [][][][][][][][] | [][][][][][][][] | | | | |
| N°2 | | | [][][][][][][][] | [][][][][][][][] | | | | |
| N°3 | | | [][][][][][][][] | [][][][][][][][] | | | | |
| N°4 | | | [][][][][][][][] | [][][][][][][][] | | | | |
| N°5 | | | [][][][][][][][] | [][][][][][][][] | | | | |

UNBLINDING: YES NO NA

| | |
|--|---|
| HAS ONE (OR SEVERAL) INVESTIGATIONAL PRODUCT(S) BEEN STOPPED?  Yes n°[][] n°[][] n°[][] n°[][] n°[][]  No  NA | HAS ONE (OR SEVERAL) INVESTIGATIONAL PRODUCT(S) BEEN REINTRODUCED?  Yes n°[][] n°[][] n°[][] n°[][] n°[][]  No  NA |
| DID THE EVENT DISAPPEAR AFTER INVESTIGATIONAL PRODUCT(S) IS STOPPED?  Yes  No  NA | DID THE EVENT REAPPEAR AFTER INVESTIGATIONAL PRODUCT(S) REINTRODUCED?  Yes  No  NA |

| | | | |
|---|---|-----------------------------|---------------------------------------|
| PROTOCOL: CHONDROG | EUDRACT: 2010-019817-20 | COUNTRY: FRANCE | |
| SPONSOR : INSTITUT BERGONIE | | INVESTIGATOR SITE : | SITE N° [] [] [] |
| DATE OF THIS REPORT : [] [] / [] [] / [] [] [] [] [] [] [] [] [] [] | INITIAL REPORT  | FOLLOW-UP REPORT N° [] [] | FINAL REPORT  |
| INCLUSION N°: [] [] SURNAME (2 LETTERS): [] [] 1 ST NAME (2 LETTERS): [] [] DATE OF BIRTH: [] [] / [] [] / [] [] [] [] [] [] [] [] [] [] | | | |

6. RADIOTHERAPY Tick if NA

| TECHNIQUE | FIELD(s) | DATES | | Dose (Gy) | |
|-----------|----------|---|---|--|---|
| | | DATE OF FIST ADMINISTRATION | DATE OF LAST ADMINISTRATION | LAST DOSE ADMINISTERED BEFORE SAE (Gy) | CUMULATIVE DOSE SINCE THE 1 ST ADMINISTRATION (Gy) |
| | | [] [] / [] [] / [] [] [] [] [] [] [] [] [] [] | [] [] / [] [] / [] [] [] [] [] [] [] [] [] [] | | |
| | | [] [] / [] [] / [] [] [] [] [] [] [] [] [] [] | [] [] / [] [] / [] [] [] [] [] [] [] [] [] [] | | |
| | | [] [] / [] [] / [] [] [] [] [] [] [] [] [] [] | [] [] / [] [] / [] [] [] [] [] [] [] [] [] [] | | |
| | | [] [] / [] [] / [] [] [] [] [] [] [] [] [] [] | [] [] / [] [] / [] [] [] [] [] [] [] [] [] [] | | |

MACHINE (SPECIFY IF POSSIBLE TRADE NAME / MODEL / SERIAL NUMBER):

| | |
|--|--|
| HAS RADIOTHERAPY BEEN STOPPED?  Yes  No  NA DID THE EVENT DISAPPEAR AFTER RADIOTHERAPY IS STOPPED?  Yes  No  NA | HAS RADIOTHERAPY BEEN REINTRODUCED?  Yes  No  NA DID THE EVENT REAPPEAR AFTER RADIOTHERAPY REINTRODUCTION?  Yes  No  NA |
|--|--|

SCENE OF EVENT: INVESTIGATOR SITE HOME HOSPITAL DAY HOSPITAL CONVALESCENT HOME
 OTHER:

7. MEDICAL DEVICE OR NON MEDICAL PRODUCT, METHOD OR ACTION Tick if NA

| DEVICE / NON MEDICINAL PRODUCT, METHOD OR ACTION | DATES OF USE |
|--|---|
| COMMON DENOMINATION: | BEGINNING DATE: [] [] / [] [] / [] [] [] [] [] [] [] [] [] [] |
| TRADE NAME (IF EC-MARKING): | END DATE: [] [] / [] [] / [] [] [] [] [] [] [] [] [] [] |
| MODEL: | VERSION (INCLUDED SOFTWARE) |
| SERIAL NUMBER | AND/OR BATCH NUMBER |
| INDICATION OF USE FOR THE PATIENT | |

| | |
|---|---|
| HAS DEVICE OR ONE (OR SEVERAL) PRODUCT(S), METHOD(S) OR ACTION(S) BEEN STOPPED?  Yes  No  NA DID THE EVENT DISAPPEAR AFTER RADIOTHERAPY STOP?  Yes  No  NA | HAS DEVICE OR ONE (OR SEVERAL) PRODUCT(S), METHOD(S) OR ACTION(S) BEEN REINTRODUCED?  Yes  No  NA DID THE EVENT REAPPEAR AFTER RADIOTHERAPY REINTRODUCTION?  Yes  No  NA |
|---|---|

SCENE OF EVENT: INVESTIGATOR SITE HOME HOSPITAL DAY HOSPITAL CONVALESCENT HOME
 OTHER:

| | | |
|--|---|--|
| PROTOCOL: CHONDROG | EUDRACT: 2010-019817-20 | COUNTRY: FRANCE |
| SPONSOR : INSTITUT BERGONIÉ | INVESTIGATOR SITE : | SITE N° [][] |
| DATE OF THIS REPORT : [][]/[][]/[][][][] | INITIAL REPORT  | FOLLOW-UP REPORT N° [][] |
| FINAL REPORT  | | |
| INCLUSION N°: [][] | SURNAME (2LETTERS): [][] | 1 ST NAME (2 LETTERS): [][] |
| DATE OF BIRTH: [][]/[][]/[][][][] | | |

